Director of the Neuropsychology Program, Rhode Island Hospital

Address: [name]

[contact]; [contact]; Email: [contact]

CODAC Behavioral Healthcare, Inc:

[name], M. D., Co-I

Research Professor, University of Rhode Island

Director of HIV and Viral Hepatitis Services and Chair of the Research Committee at CODAC Behavioral Healthcare

Address: CODAC Behavioral Healthcare, Inc., [name]

[contact]; [contact]; Email: [contact]

PRÉCIS

Study Title

Optimization and Multi-Site Feasibility of Yoga for Chronic Pain in People in Treatment for Opioid Use Disorder

Objectives

Our project will have two phases. Specific aims for each phase are:

Phase 1 – MOST Preparation Phase:

1. To conduct a pilot trial at two new OAT clinic sites, enrolling n=10 at both sites, for a total n=20.
2. Establish clinical trial procedures and document feasibility at both sites prior to conducting a fully powered optimization trial.
3. Demonstrate our ability to a) recruit participants; b) train yoga teachers to fidelity; c) randomize participants to intervention components and correctly administer components; d) run classes; and e) collect follow-up assessments.

Phase 2 – MOST Optimization Phase:

1. To conduct a 2x2x2x2 factorial experiment that will allow us to evaluate the impact of each of the 4 intervention components on yoga dosage received. We plan to enroll a total n=192. All participants will receive the core yoga intervention, with random assignment to the additional four intervention components.
2. Use results from Phase 2 to choose an efficient combination of intervention components that, together with standard yoga classes, maximizes yoga dosage.
3. Examine mechanisms by which components are hypothesized to work.

The primary objective for this project is to develop an efficient combination of intervention components that, together with standard yoga classes, maximizes yoga dosage. We will also be able to examine mechanisms by which components are hypothesized to work.

Design and Outcomes

In Phase 1, we will conduct a pilot trial of our standard yoga intervention and four intervention components to demonstrate feasibility. Participants will be patients engaged in opioid agonist therapy (OAT) with chronic pain.

In Phase 2, we will conduct a factorial RCT to evaluate the impact of each of the 4 intervention components on yoga dosage received. Participants will be patients engaged in opioid agonist therapy (OAT) with chronic pain.

Interventions and Duration

Yoga classes. Participants will be asked to attend one class (approximately 45-60 mins long) per week for 12 weeks. Classes will be either in person or over a secure video-based platform, such as Zoom. Participants in Phase 1 will participate for 3 months (12 weeks of intervention, 3 month follow up interview at end of treatment). Participants in Phase 2 will participate for 12 months (12 weeks of intervention, 9 months of follow up).

Component 1: Participants will be randomized to receive or not receive personal practice videos featuring study yoga teachers.

Component 2: Participants will be randomized to receive or not receive initial and 1-month 1:1 sessions with a yoga teacher. Sessions will either be in person or over a secure video-based platform.

Component 3: Participants will be randomized to receive or not receive text messages cuing personal practice.

Component 4: Participants will be randomized to receive or not receive monetary incentives for class attendance.

Sample Size and Population

The proposed project will include up to 20 participants in a pilot trial (Phase 1), and 192 participants in a factorial randomized controlled trial (Phase 2). Participants will be individuals engaged in OAT with chronic pain aged 18 or over, regardless of gender.

1. STUDY OBJECTIVES

1.1 Primary Objective

Our project will have two phases. Specific aims for each phase are:

Phase 1 – MOST Preparation Phase:

1. To conduct a pilot trial at two new OAT clinic sites, enrolling n=10 at both sites, for a total n=20.
2. Establish clinical trial procedures and document feasibility at both sites prior to conducting a fully powered optimization trial.
3. Demonstrate our ability to a) recruit participants; b) train yoga teachers to fidelity; c) randomize participants to intervention components and correctly administer components; d) run classes; and e) collect follow-up assessments.

Phase 2 – MOST Optimization Phase:

4. To conduct a factorial experiment that will allow us to evaluate the impact of each of the 4 intervention components on yoga dosage received. We will enroll a total n=192. All participants will receive the core yoga intervention, with random assignment to the four intervention components outlined above.
5. Use results from Phase 2 to choose an efficient combination of intervention components that, together with standard yoga classes, maximizes yoga dosage.
6. Examine mechanisms by which components are hypothesized to work.

2. BACKGROUND AND RATIONALE

2.1 Chronic pain in people receiving OAT

Chronic pain is a significant problem for at least half of all persons receiving opioid agonist therapy (OAT) for opioid use disorder – i.e., buprenorphine/ naloxone (BUP) or methadone maintenance treatment (MMT). In OAT patients, chronic pain is associated with disability, psychiatric disorders, physical problems, and increased misuse of opioids or other illicit drugs. Behavioral interventions, such as CBT, mindfulness-based interventions, or yoga may be useful adjunctive interventions for decreasing pain-related disability. Hatha yoga may be a useful adjunctive approach for decreasing pain-related disability and pain severity, and preventing opioid misuse during OAT. There is evidence supporting its efficacy in other chronic pain populations, and yoga may target cravings and other risk factors for opioid relapse. It is essential that a future efficacy trial employ an intervention that is efficient, economical and scalable, but that allows (and encourages) participants to receive a “dosage” of yoga sufficient to adequately test the hypothesis that yoga is effective, i.e., reduces pain interference, and improves other pain and substance use outcomes.

2.2 Study Rationale

Yoga is an ancient Indian system of philosophy and practice¹. Most U.S. practitioners practice *hatha* yoga, which includes physical postures (*āsanas*), breath control (*prāṇāyāma*), and meditative practices. (In this proposal, when we refer to yoga, we are referring to *hatha* yoga). A meta-analysis of yoga across chronic pain conditions (including back pain, headache, rheumatoid arthritis, n = 16 studies) reported that yoga had a moderate-large effect on pain². Yoga also had a moderate-large impact on pain-related disability and a moderate impact on depressed mood (SMD = -0.65)².

There are various plausible mechanisms by which yoga may have an impact on individuals with chronic pain. First, yoga may promote mindfulness in everyday life. Mindfulness practices may help people with chronic pain experience the sensory component of pain with less negative affect, leading to better quality of life and less pain-related interference. Second, yoga may decrease pain catastrophizing^{3,4}, in which patients develop a disproportionate interpretation of chronic pain as calamitous and threatening, leading to avoidance of physical and other activities⁵. Amongst OAT patients, pain catastrophizing is associated with increased risk for opioid misuse^{6,7}, increased craving⁸, and more pain-related disability⁹. Engaging in yoga may help people who have feared exercise to start engaging in gentle physical activity again. Third, yoga may have a direct impact on mood symptoms that often co-occur with pain such as depression or anxiety¹⁰⁻¹² which are common in people with opioid use disorder^{13,14} and are associated with increased risk for opioid or other substance misuse¹⁵⁻¹⁷. Finally, *hatha* yoga may serve to increase overall physical activity. Yoga may improve core and other muscle strength as well as endurance¹⁸.

Yoga is increasingly popular and available, with the percent of US adults practicing yoga increasing from 8.9% in 2012¹⁹ to 14.3% in 2017²⁰. Yoga is increasingly being offered at addiction treatment centers^{21,22}. Yoga can also be adjunctive to other pain and substance use treatment. Yoga classes may also be structured in such a way to allow for rolling rather than cohort enrollment, thus increasing access.

Although yoga has been recommended as a complementary treatment²³, there are few studies of yoga for people with substance use disorders²⁴, including a few feasibility studies^{25,26}. The only study of which we are aware that *hatha* yoga for OAT patients with chronic pain is our pilot project. In brief, we assessed feasibility and acceptability of a 12-week manualized yoga program (vs. a 12-week health education program) in OAT patients with chronic pain. Our pilot study was largely successful, showing excellent feasibility for recruitment, instructor fidelity, and participant retention in follow-up assessments. Our primary challenge was in class attendance, a common problem with behavioral interventions for OAT patients²⁷⁻²⁹.

3. STUDY DESIGN

In Phase 1, we will enroll 10 participants at each recruitment site (n=20). The purpose of Phase 1 (MOST Preparation Phase) is to allow us to establish and refine procedures at these new sites and document aspects of feasibility, including our ability to a) recruit participants; b) train yoga teachers to fidelity; c) randomize participants to intervention components and correctly administer these components; d) run classes; and e) collect follow-up assessments. Enrollment period for this phase will last approximately 4 months.

In Phase 2, we will conduct a fully powered optimization trial. We will enroll 192 participants, planning to role approximately equal numbers of participants in both sites. In both phases, all participants will receive the core yoga intervention (12 weeks of weekly manualized yoga classes), with random assignment to the 4 key intervention components. Participants will be patients enrolled in methadone or buprenorphine/naloxone treatment with chronic pain. Enrollment period for this phase will last approximately 2 years.

4. SELECTION AND ENROLLMENT OF PARTICIPANTS

4.1 Inclusion Criteria

Participants must meet all of the relevant inclusion criteria to participate in the study.

Inclusion Criteria - Phase 1 and 2

- 1) Enrolled in MMT or BUP treatment for > 3 months
- 2) Plan to continue treatment for next 6 months
- 3) Chronic pain, defined as pain for at least half the days over the previous three months, a mean score of 4 or higher on the BPI Pain Interference Scale (with reference to chronic pain), and pain severity of 4 or higher on a Visual Analog Scale (0-10) indicating “worst pain in the last week.” Pain severity score will also refer to the areas of their body in which they have chronic pain.
- 4) Aged ≥ 18
- 5) Proficiency in English sufficient to engage in informed consent in English, understand classes taught in English, and read short sentences
- 6) Available at least one of the times study classes are offered.

4.2 Exclusion Criteria

All participants meeting any of the exclusion criteria at baseline will be excluded from study participation.

Exclusion Criteria - Phase 1 and 2

- 1) Currently taking yoga classes or practicing yoga at home once per week or more often.
- 2) Medical conditions that would make participation in yoga unsafe or not possible, including active malignancy treatment, fracture, recent joint surgery, use of assistive ambulatory devices other than a cane. . (In cases where this is unclear, site PI will make final determination based on available evidence.)
- 3) Severe or progressive neurologic deficits. (In cases where this is unclear, site PI will make final determination based on available evidence.)
- 4) Other severe disabling chronic medical and/or psychiatric comorbidities deemed by the site PI on a case-by-case basis to prevent safe or adequate participation in the study (e.g., cognitive impairment that prevents a participant from understanding assessments; history of disruptive behavior in medical settings; severe disabling heart failure or lung disease)
- 5) Surgery requiring overnight hospitalization planned in the next 3 months
- 6) Pregnancy
- 7) Plan to move out of the area within 6 months.

- 8) Homeless, defined as any time in the past month sleeping in a shelter or on the street.

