5.2 Handling of Study Interventions

Yoga Intervention

Yoga classes. All participants will receive the manualized hatha yoga program. Participants will be asked to attend one 60-minute class per week for 12 weeks in person or via a secure video-based platform. Each class will consist of: greeting and discussion of personal practice; centering and breath awareness; pranayama (breathing practices); warm up movements; an asana sequence; a seated meditation; and discussion of personal practice. Classes will acknowledge the validity of participants' pain and gently challenge them to try a new way of coping with it; emphasize breathing in every part of the class; and run the class at a slow pace. Class size will range between 1 and 12 participants.

Yoga Personal practice. Personal practice will be essential for increasing yoga "dosage." When participants first start class, we will give them a yoga mat to take home, a curated list of YouTube videos, and written instructions for personal practices that can be used to manage pain and cope with urges to misuse opioids and other substances. In each class, the yoga instructor will review specific practices and recommend that participants try those practices at home. The practices will always be ones that carry with it minimal risk of injury, and instructors will go over safe practice in class. Participants may continue in the study regardless of whether they practice at home.

Intervention Component 1: Personal practice Videos Featuring Study Yoga Teachers. As part of the standardized yoga intervention, all participants will receive a curated list of YouTube videos for yoga personal practice. However, participants randomized to receive component 1 will also receive study-specific videos of varying lengths featuring study teachers and only yoga practices taught in class. Participants will be randomized to either receive or not receive study-specific videos.

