6. STUDY PROCEDURES

6.1 Schedule of Evaluations

Table 1: Assessment schedule for Phase 1 and Phase 2

Assessment	Type of Assessment	Screening: (Up to 30 days before BL1)	Baseline Visit 1	After initial class	Weekly M1, M2, M3	M1 visit	M2 visit	M3 visit	M6 visit (Phase 2 only)	M12 visit (Phase 2 only)
Inclusion/Exclusion	Interview, pre-randomize.	X	X							
Informed Consent Form	Pre-randomize.		X							
Enrollment and Randomization	Interview		X							
Credibility Expectancy Questionnaire (CEQ)	Self-report			X						
Homework Questionnaire	Self-report				X				X	X
Injuries due to yoga	Self-report				X					
Systematic Assessment for Treatment Emergent Events (SAFTEE)	Interview								X	
Chart Review	Chart Review		X		X				X	X
Other Adverse Events	Interview		X		X	X	X	X	X	X
SUD, psychiatric, sleep, and pain medications (modified TRAQ)	Interview		X					X	X	X
Tampa Scale of Kinesiophobia (TSK)	Self-report		X			X	X	X		
Self-efficacy for exercise	Self-report		X			X	X	X		
Logistic Factors	Self-report		X			X	X	X		
Behavioral Regulation in Exercise Questionnaire (BREQ-2), modified for yoga	Self-report		X			X	X	X		

Assessment	Type of Assessment	Screening: (Up to 30 days before BL1)	Baseline Visit 1	After initial class	Weekly M1, M2, M3	M1 visit	M2 visit	M3 visit	M6 visit (Phase 2 only)	M12 visit (Phase 2 only)
Brief Pain Inventory (BPI)*	Self-report		X			X	X	X	X	X
Numerical Rating Scale (NRS), Pain Severity	Self-report		X			X	X	X	X	X
WHO Quality of Life, Brief Version (WHOQOL-BREF)	Self-report		X					X	X	X
PROMIS Depression Scale	Self-report		X					X	X	X
PROMIS Anxiety Scale	Self-report		X					X	X	X
Addiction Severity Index (ASI)	Interview		X			X	X	X	X	X
Penn Craving Scale	Self-report		X			X	X	X	X	X
Demographics	Self-report, blind DB		X							
Review of Medical Comorbidities	Self-Report		X							
Qualitative Exit Interview (Phase 1 only)	Interview							X		
Payment			\$10			\$20	\$20	\$30 (assmt) + \$35 (return of study cell phone)	\$30	\$40

* When calculating the BPI- Pain Interference Scale, we will not include the “work” item, as we anticipate that this item does not apply to a large proportion of our sample.

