6.2.1 Screening Evaluation

Consenting Procedure

All phases will have a) agreement from individual to conduct brief eligibility screening and b) informed consent individual at the first visit.

For information about agreement to screening, please see section 4.3 Study Enrollment Procedures.

Screening

For Phases 1 and 2, because all inclusion criteria are verified or re-verified at BL the screen may be conducted as many as 30 days prior to BL.

6.2.2 Baseline – Phase 1 and Phase 2

Consenting Procedure

Informed consent will be obtained at the baseline appointment.

Please see section 4.3 for more information about the consent procedures.

Documents will be stored in a locked file cabinet, or will be located in REDCap.

In-Person Screening

After informed consent/assent is complete, RAs will administer the following to ascertain inclusion criteria during BL1:

- BPI –Pain Interference
- NRS– Average and worst pain in the past week
- Review of Medical Comorbidities

If participants meet all eligibility criteria, we will then conduct the remainder of the BL assessments.

For participants who do not meet eligibility criteria, we will inform the individual without
Protocol Version 1.5

stating specific reason for exclusion. We will provide referrals to the community upon request.

Baseline Assessments – Phases 2 and 3

Remaining Baseline1 assessments include:

- TRAQ
- TSK
- Self-Efficacy for exercise
- Logistic Factors (from Cardiac Rehabilitation Barriers Scale)
- BREQ-2
- WHOQOL-BREF
- PROMIS® Depression Scale
- PROMIS® Anxiety Scale
- ASI
- Penn Craving Scale
- Demographics

Randomization

Allowable window between BL1 and randomization is 14 days. Participants are considered enrolled after randomization. The participant is invited to begin the study intervention within 1 week of randomization.

Payment

Payment to participants for completion of this visit is \$10.

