9.5 Outcomes

9.5.1 Primary/Proximal Outcome

Phase 1 is a pilot study to assess feasibility. The primary aims and outcome assessments are shown in Table 4 below.

Table 4. Targets for Phase 1 Pilot Study.		
Feasibility Area	Method of assessment	Target at each site
Recruit participants	Number recruited per month	Recruit 10 participants in 4 months.

Train yoga teachers to fidelity	Teacher fidelity scale	Each teacher demonstrates >80% fidelity on final 3 classes rated.
Randomize participants to intervention components and correctly administer these components	Randomization errors; receipt of incorrect intervention components	No errors/ incorrect components received in 2 nd half of participants randomized.
Collect follow-up assessments	Percent of follow-up assessments collected (for M1, M2, and M3)	≥ 70% with sufficient data collected on dosage; ≥ 70% of other follow-up assessments collected, including chart reviews

The proximal outcome of Phase 2 is yoga dosage received. This will be calculated by adding total number of minutes per week in the study yoga class and total number of minutes per week in personal practice (or outside yoga classes). Research staff will take attendance at study yoga classes, and, in the event someone does not attend the entire yoga class, will record the number of minutes present in class. We will measure personal practice using the Weekly Personal practice Questionnaire.

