Once data collection is complete, we will convene a meeting (or conference call) to make decisions about which intervention components should be included in the final intervention package. Participants in this meeting will include:

1. MPIs and co-Is and consultant [name];
2. Selected NCCIH staff (e.g., PO); and
3. Selected yoga instructors

At this meeting we will review all data collected.

Step 1: For each intervention component, we will first review the main and 2nd order interaction effects from the factorial experiment on the primary outcome of number of yoga minutes per week. We assume data will be missing at random. Missing data will be addressed using multiple imputation by chained equations.³³ Because the goal is intervention optimization, retention of components will not be based on a single criterion. We will initially choose to include all components for which there is a main or sympathetic interaction effect with a) an effect size (SMD) of 0.40 (estimated, based on preliminary data, to be 31 mins of yoga per week) or greater favoring the component; OR b) $p < .10$ favoring the component OR c) if the estimated Bayes factor provides substantial or stronger evidence preferring the intervention hypothesis to the hypothesis of no treatment effect. (See below for more information on Bayes factor).

Special cases:

1. Of monetary incentives for class attendance, we will look specifically at class attendance. If monetary incentives increase class attendance, and do not decrease overall minutes of practice, we will choose to include.
2. 3rd and 4th order interactions may be tricky to interpret. We will look at them, but place priority on main effects and 2nd order interactions in making decisions.
3. It is possible that 2nd order interactions may be antagonistic where the combination of two or more components is less effective than would be expected based on the main effects alone. At the same time, there may be significant positive main effects for both components. In this case, we will examine graphical depictions of results in order to determine whether to include both of the two components in question.

Step 2: All components that pass Step 1 will then be examined in light of their feasibility and acceptability. Data that bear on feasibility and acceptability include:

1. Participants' responses to qualitative interviews
2. Yoga instructors' experiences (field notes)

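### The Phase 2 primary outcome, yoga minutes per week, has no baseline value, so less-than-weekly prior practice can count as dosage unrecorded and unadjusted: a small precision gap, not a bias

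*Combined protocol and SAP*

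**What the plan says.** **Eligibility.** Exclusion 1 in section 4.2 is worded by frequency: "Currently taking yoga classes or practicing yoga at home once per week or more often". The sentence does not settle whether the weekly limit applies to classes as well as to home practice.

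**Outcome.** Section 9.5.1 adds minutes in the study class to "total number of minutes per week in personal practice (or outside yoga classes"). Nothing is subtracted for practice that predates enrolment. On the source of the minutes it says "We will measure personal practice using the Weekly Personal practice Questionnaire". Table 1 has no row of that name. I take the row called "Homework Questionnaire" to be the same instrument.

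**Timing.** Table 1 and the visit lists in section 6.2.4 place that questionnaire weekly during the 12 weeks, at month 6 and at month 12. There is no baseline mark. In section 6.2.2, the list introduced by "RAs will administer the following to ascertain inclusion criteria during BL1" holds the BPI interference scale, the pain NRS and medical comorbidities. The remaining baseline list has no measure of yoga practice. Pain, mood, craving, kinesiophobia, exercise self-efficacy and motivation all have baseline values.

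**Analysis.** Section 9.6 fits a general linear model with effect-coded components and four covariates: site, sex, age and OAT type. Prior practice is not among them.

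**The concern.** Eligibility counts sessions and the outcome counts minutes, and no measurement before randomisation links the two. A person who practises less than weekly is eligible, may carry on, and has those minutes added to dosage. At the end, the analyst cannot tell how much of the recorded practice was already there, cannot check whether it was balanced across the levels of a component, and cannot adjust for it.

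Three things are at stake: some precision in the component effects, the meaning of the absolute dosage figure, and the ability to inspect balance on the variable closest to the outcome. Precision has some weight here because section 9.2 argues that a Type II error may do as much harm as a Type I error in an optimisation trial. A baseline value cannot be recovered reliably once participants know their components.

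**Working it through.** **Inputs from the documents.** Analysed N = 158, so n = 79 per level of each component (9.2, 9.6). Planned standardised difference d = 0.40, described as "estimated, based on preliminary data, to be 31 mins of yoga per week" (9.6, Step 1). The implied SD is 31/0.40 = 77.5 min/week.

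**1. Reproduce the stated power.** Power = Φ(d√(n/2) − z).
- Section 9.2 writes α/2 = .10. With two-sided 0.10, z = 1.645.
- d = 0.40: 0.40 × √39.5 = 2.514; 2.514 − 1.645 = 0.869; power 0.808.
- d = 0.50: 3.142 − 1.645 = 1.498; power 0.933.
- Both match the stated figures (above .80 and above .90).
- Required n per level: 2(1.645 + 0.842)²/0.40² = 77.3, so 78 against 79 planned.
- If α is instead read as one-sided 0.10, power at d = 0.40 is 0.891 and there is more slack.

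**2. What Exclusion 1 lets through.** Minutes per week = session length × 7 / days between sessions.
- 60 min every 8 days: 52.5
- 60 min every 10 days: 42
- 60 min every 14 days: 30
- 30 min every 14 days: 15

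So non-trivial practice can pass, but only as fairly long sessions spaced more than a week apart.

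**3. Effect on the comparison.** Assume a share q of entrants carries c min/week on top of the SD of 77.5. The documents give neither q nor c. I take q = 5–20% and c = 31–52.5.

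| Quantity | q = 5%, c = 31 | q = 20%, c = 52.5 |
|---|---|---|
| Rise in mean at both levels, qc | 1.6 min/week | 10.5 min/week |
| Added variance, q(1−q)c² | 45.6 | 441 |
| As a share of 77.5² = 6006 | 0.8% | 7.3% |
| SE of chance imbalance, √(2 × added variance/79) | 1.1 min | 3.3 min |
| Power at 31 min/week | 0.805 | 0.783 |

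The SE of a component effect is 77.5 × √(2/79) = 12.3 min, so the chance imbalance is small beside it. A simulation with 10% of entrants at 52.5 min/week and N = 160 gave a mean bias of 0.06 min. Its two-sided type I error was 0.0985 at nominal 0.10. If the preliminary-data SD of 77.5 already contains such practice, the loss in the last row is not additional.

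**4. Gain from a baseline covariate.** With correlation r between baseline minutes and dosage, replace d by d/√(1 − r²). The minimum detectable difference is (1.645 + 0.842) × √(2/79) × √(1 − r²) × 77.5.

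| r (assumed) | Power at d = 0.40 | Minimum detectable difference, 80% power |
|---|---|---|
| 0 | 0.808 | 30.7 min/week |
| 0.15 | 0.815 | 30.3 min/week |
| 0.30 | 0.839 | 29.2 min/week |

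Exclusion 1 keeps most baseline values near zero, which restricts the range and makes a low r more likely.

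**The case against.** The strongest defence is that the outcome is yoga received, a total and not a change score, and that outside classes are included on purpose. Continued practice is then genuine dosage. That largely stands. It still leaves the absolute level as a mixture of prompted and pre-existing practice that cannot be separated.

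Second, anyone practising weekly or more is already out, and the components are randomised among people who all receive core yoga. Prior practice therefore falls equally on both levels in expectation, and chance imbalance is already covered by the standard error. This stands in full and limits the point to precision and description.

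Third, the instrument list in section 6.2.2 does not show that Exclusion 1 goes unchecked, because Table 1 has a separate inclusion/exclusion interview at screening and baseline. This also stands. What is missing is a recorded number of minutes.

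A reader might infer three stronger things that the documents do not support:
- That an entrant whose own practice exceeds 31 min/week defeats the decision rule. That figure is a mean difference between randomised levels and one of three alternative Step 1 criteria. It is not a ceiling on a person's minutes.
- That someone with a daily breathing or meditation habit is eligible as written. Classes do teach "pranayama (breathing practices); warm up movements; an asana sequence; a seated meditation", but section 2.2 defines yoga to include breath control and meditative practices, so such yoga practice falls under Exclusion 1. What remains is possible misunderstanding of a screening question whose wording is not in the documents.
- That Exclusion 1 needs a limit in minutes. Nothing in the documents shows a need for one.

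**Conclusion.** The point holds as a minor gap in precision and description. The primary outcome has no baseline value, the model has no prior-practice covariate, and less-than-weekly practice can enter the dosage total. Component effects and the Step 1 decision are not biased.

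Under the assumed shares and amounts, power falls from 0.808 by at most about 0.025 and mean dosage rises by 1.6 to 10.5 min/week at both levels of every component. A baseline covariate would probably add between nothing and 0.03 to power (0.808 to 0.839 for r from 0 to 0.30). These figures rest on two-sided α of 0.10, the SD of 77.5 implied by the plan, and assumed values of q, c and r. The margin of 79 against 78 per level makes the small gain worth having, but does not make the gap serious.

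**What to change.** - Give the practice questionnaire, or a short minutes-per-week version of it, at Baseline Visit 1 before randomisation. Mark it in the baseline column of Table 1 and list it in section 6.2.2.
- Use the section 2.2 definition of yoga (postures, breath control, meditative practices) for the screening question, the baseline item and the scoring of dosage.
- State in section 4.2 whether the weekly limit in Exclusion 1 applies to classes as well as to home practice.
- Add baseline yoga minutes to the prespecified covariates in section 9.6, and report them by component level with the baseline data.
- Use one name for the questionnaire in Table 1 and section 9.5.1.

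The cost is a few minutes of participant time at an existing visit and one residual degree of freedom out of about 138 (158 less 16 factorial terms and 4 covariates).
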